10.6 Follow-up of Adverse Events

After the initial report, the investigator is required to proactively follow up with each subject and provide further information on the subject's condition.

All AEs (serious and non-serious) will be followed until resolution, until the condition stabilizes, until the event is otherwise explained, or until the subject is lost to follow-up.

The investigator is obligated to perform or arrange for the conduct of supplemental measurements and/or evaluations as may be indicated or as requested by GSK CH to elucidate as fully as possible the nature and/or causality of the AE. This may include additional laboratory tests or investigations, histopathological examinations, or consultation with other health care professionals.

New or updated information will be recorded on the AE CRF page and on the SAE form (subject to the classification of the AE).

The investigator will submit any updated SAE data to GSK CH within 24 hours of receipt of the information.

Investigators are not obliged to actively seek AEs in former subjects. However, if the investigator learns of a SAE, including death, at any time after a subject has been discharged from the study, and considers the event reasonably related to the study product or study participation, the investigator will promptly notify GSK CH by emailing the information to the GSK CH Clinical Operations Safety Reporting email box PPD

The GSK CH Study Manager or designee will be responsible for forwarding the information to the Case Management Group, Global Clinical Safety and Pharmacovigilance group mailbox at GSK PPD

The investigator will submit any updated SAE data to GSK CH within the designated reporting time frames.

10.7 Withdrawal Due to an Adverse Event

Withdrawal due to AEs should be distinguished from withdrawal due to other causes, according to the definition of an AE noted earlier, and recorded on the appropriate AE CRF page.

When a subject withdraws because of an SAE, the SAE must be reported in accordance with the reporting requirements defined.

10.7.1 Sponsor's Reporting Requirements to Regulatory Authorities and Ethics Committees

GSK CH has a legal responsibility to notify, as appropriate, the local regulatory authority and other regulatory authorities about the safety of a product under clinical investigation. Prompt notification of SAEs by the investigator to GSK CH is essential so that legal obligations and ethical responsibilities towards the safety of subjects are met.

GSK CH will comply with country specific regulatory requirements relating to safety reporting to the regulatory authority, IRB/EC and investigators.

Protocol Number: 209638 Draft Clinical Protocol

Investigator safety reports must be prepared for suspected unexpected serious adverse reactions (SUSAR) according to local regulatory requirements and sponsor policy and forwarded to investigators as necessary.

An investigator who receives an investigator safety report describing a SAE or other specific safety information e.g. summary or listing of SAE from the sponsor will review and then file it along with the Investigator's Brochure in the investigator study master file, and will notify the IRB/IEC, if appropriate according to local requirements.

10.8 Pregnancy

10.8.1 Time Period for Collecting Pregnancy Information

Pregnancy information will be collected on all pregnancies reported while a female subject is participating in the study from the signing of informed consent until 5 days after last administration of study product.

10.8.2 Action to be Taken if Pregnancy Occurs

The investigator will record pregnancy information on the appropriate form scan and e-mail it to the GSK CH Clinical Operations Safety Reporting email box PPD within 24 hours of learning of the subject becoming pregnant. The GSK CH Study Manager or designee will be responsible for forwarding the pregnancy form to the Case Management Group, Global Clinical Safety and Pharmacovigilance mailbox PPD Original pregnancy information forms will be retained in the investigator study master file.

The subject will be followed to determine the outcome of the pregnancy. Information on the status of the mother and infant / neonate (including concomitant medications taken by the mother during the pregnancy) will be forwarded by the investigator to the GSK CH Clinical Operations Safety Reporting email box and the GSK CH Study Manager or designee will forward this information to the Case Management Group, Global Clinical Safety and Pharmacovigilance group mailbox at GSK PPD Generally, follow-up will be no longer than 6 to 8 weeks following the estimated delivery date. Any termination of the pregnancy will be reported.

While pregnancy itself is not considered to be an AE, abnormal pregnancy outcomes (e.g. spontaneous abortion, fetal death, stillbirth, congenital anomalies, ectopic pregnancy) are, and should be recorded as an SAE.

Any female subject who becomes pregnant while participating will be withdrawn from the study.

11 DATA MANAGEMENT

As used in this protocol, the term CRF is understood to refer to either a paper form or an electronic data record or both, depending on the data collection method.

For this study, subject data will be entered into an electronic CRF (eCRF), using a validated system. Data relating to SAEs, pregnancy and incidents will also be collected on paper forms.

The investigator is responsible for verifying that data entries are accurate and correct by physically or electronically signing the CRF.

The source documents (e.g. hospital records, clinical and office charts, laboratory notes, memoranda, subject diaries, questionnaires, evaluation checklists, pharmacy dispensing records,

Protocol Number: 209638 Draft Clinical Protocol

recorded data from automated instruments, microfiches, photographic negatives, microfilm or magnetic media, x-rays, subject files and records kept at the pharmacy, at the laboratory and at the medico-technical departments involved in the clinical study) which contain the source of data recorded in the CRF should be specified in Section 8 and 9. The CRF can be used as a source document at the discretion of data management.

Each subject will be assigned and identified by a unique Screening Subject Number. Any reference made to an individual subject within the study must be done using their unique Screening Subject Number.

11.1 Case Report Form

A CRF is a printed, optical, or electronic document designed to record the protocol required information to be reported to the sponsor on each trial subject.

For each subject who has given informed consent/assent the CRF must be completed and signed by the Principal Investigator (or authorized designee) to certify that the data are complete and correct. The investigator must maintain accurate documentation (source data) that supports the information entered in the CRF.

Management of clinical data will be performed in accordance with Third Party BDM Vendor applicable standards and data cleaning procedures with oversight by GSK CH to ensure integrity of the data, for example, to remove errors and inconsistencies in the data.

To protect the privacy of subjects, no Personally Identifiable Information (PII) (including the subject's name or initials or full birth date) is to be recorded in the CRF or as part of the query text.

All CRF pages should be completed during a subject assessment when the CRF has been designated as the source. Data that is sourced elsewhere should be entered into the CRF in an agreed upon timeframe between the Investigator and Sponsor.

GSK CH will obtain and retain all CRFs and associated study data as applicable at the completion of the study.

11.2 Data Handling

Documentation of all data management activities should allow step-by-step retrospective assessment of data quality and study performance.

Any changes or corrections to data will be performed in the Electronic Data Capture (EDC) System, and it will include rationale for changes. The EDC system has an audit trail, which will provide a complete record of the changes and corrections endorsed by the Investigator.

Adverse events will be coded using Medical Dictionary for Regulatory Activities (MedDRA) and any concomitant medications terms (if applicable) using an internal validated medication dictionary, GSKDrug.

11.2.1 Data Queries

Programmed edit checks will be generated automatically, as the data are being entered into the system. Reports and listings on the CRF data will also be run, in addition to the queries already programmed and generated by the system, to raise manual queries as needed for site clarification or correction. The Clinical Dictionary Development and Management Group will raise queries as needed on safety data to code the terms (AEs and Drugs or concomitant medication) appropriately.

Protocol Number: 209638 Draft Clinical Protocol

The study monitor will perform ongoing review of the CRFs in accordance with the monitoring plan, to confirm that data entered into the CRF by authorized site personnel are accurate, complete, and verifiable from source documents; that the safety and rights of participants are being protected; and that the study is being conducted in accordance with the currently approved protocol and any other study agreements, ICH GCP, and all applicable regulatory requirements.

Any queries will be generated in the EDC System to the Investigator or designee, enabling the errors to be addressed in parallel with Data Management review. The study monitor can also run reports and listings on the CRFs, to raise manual queries as needed for site clarification or correction.

11.3 Processing Patient Reported Outcomes

Paper based patient reported outcome (PRO) data may be collected from a diary, questionnaire, or other specified document, etc. and entered into the data management system (DMS).

Electronic Patient reported outcome (ePRO) data may be collected using electronic devices and transferred electronically to GSKCH or Third-party DM vendor.

All PRO source data should be reviewed by the study staff and the study monitor in order to ensure accurate transcription of data and that any potential AEs or concomitant medications reported on these documents are discussed with the subject and transcribed accurately to the CRF and/or DMS. PROs that are classed as source data will be retained by the investigator and true/certified copies may be sent to a designated vendor or GSK CH as required.

To protect the privacy of subjects, no Personally Identifiable Information (PII) (including the subject's name or initials or birth date) is to be recorded on any PRO/ePRO that will be forwarded to GSK CH or Third-Party Vendor.

In this study subjects will be provided with a paper diary card to complete during the washout and home use period. Subject self-assessment responses will be collected directly in the CRF.

11.4 External Data

External Data are subject data obtained externally to the CRF. These data are generated from laboratory instruments, computers or other sources and then transcribed into a file and format agreed upon by GSK CH to identify the subject and time point referenced in the CRF and/or protocol.

An agreed quality control process will be performed against the transcribed data to the source to ensure the accuracy of the transcription. The transcribed data is transmitted in an agreed upon format to GSK CH.

Reconciliation will be performed between the transcribed data and the clinical database to ensure subject and time point referenced in the Clinical Database match before Clinical Database Freeze (locking of the database) can occur.

12 STATISTICAL CONSIDERATIONS AND DATA ANALYSES

12.1 Sample Size Determination

The sample size is determined with the success criteria of the study in mind, that each developmental product will be significantly beneficial (superior) on change from baseline in TEWL measurements following 28 days twice daily use on the face.

Protocol Number: 209638 Draft Clinical Protocol

The distributional assumptions underlying the calculations are taken from the pilot study (GSK data on file) for which change from baseline (BL) in TEWL for the face is used. The leg responses for this study are secondary and not considered in the sample size estimation. From the pilot study it is expected that leg treatment effects will be larger and also variability reduced compared to face values.

In the pilot study the mean change from baseline between active (test moisturizers) and control (soap only) groups in terms of face TEWL at Day 29 was -1.24. Each subject will receive a pair of products to be applied randomly to Left/Right or Right/Left sides consistently throughout the trial. The primary response will therefore be a pair of changes from BL in face TEWL for each test product vs. a control (soap only). The square root of the Mean Square Error (MSE) from the analysis of the pilot study is estimated as 2.199, with 60 subjects directly comparing test product with control with a mean difference in change from BL face TEWL of -1.24 the power to detect such a difference at the two-sided 5% significance level is approximately 86%. Via a simulation study (50,000 simulated studies) we can allow each group of 60 subjects receiving a test product to be compared to 120 subjects who receive control (soap only), 60 who received the test product, and 60 who got the other test product, so some contributions are within subject and some between. This results in an estimated power for any single test product versus control (soap only) of approximately 89.2% and for both test products to achieve significance of 80.0%.

The study is therefore powered (89%) to ensure individual treatments result in significant improvement in TEWL at Day 29 on the face compared to soap alone. For both test treatments to reach success it is estimated that there is 80% power.

12.2 Statistical Methods and Analytical Plan

Additional details of the proposed statistical analysis will be documented in the statistical reporting and analysis plan (RAP), which will be written following finalization of the protocol and prior to study unblinding.

12.2.1 Definition of Analysis Populations

- The Safety population will comprise all randomized subjects who receive at least one dose of the study product. This population will be based on the product the subject actually received.
- The (Modified) Intent-To-Treat (MITT) population will comprise all randomized subjects who receive at least one dose of study product and have at least one post randomized assessment of efficacy. This population will be based on the study product to which the subject was randomized. Any subject who receives a randomization number will be considered to have been randomized.
- The PP population includes all MITT subjects who fully comply with all study procedures and restrictions. Deviations will be determined and applied prior to unblinding and consist of variations in criteria likely to affect the interpretation of the efficacy parameters.

Protocol Number: 209638 Draft Clinical Protocol

12.2.2 Exclusion of Data from Analysis

Exclusion of any data from the analyses will be determined during a Blind Data Review Meeting prior to database lock. Any reasons for exclusion from an analysis population will be listed, if applicable.

12.2.3 Demographic and Baseline Characteristics

Age and other continuous demographic and clinical (e.g. Clinical and Subject assessment of skin dryness) baseline variables will be summarized using descriptive statistics such as means, medians and standard deviation. Gender, race and other categorical demographic and clinical (e.g. Fitzpatrick Skin Type) baseline variables will be summarized using frequency counts and percentages for the safety and ITT populations.

12.2.4 Study Product Compliance

Compliance with the planned study product use will be tabulated and summarized for the safety and ITT populations.

12.2.5 Prior and Concomitant Medications

Prior medications, concomitant medications and significant non-drug therapies taken during treatment will be listed for the safety population.

12.2.6 Primary Analysis(es)

The primary means of assessing the outcome of the study is the analysis of the change from BL in TEWL (face) of each of the two developmental products, compared to standard soap use only, at Day 29.

Secondary analysis will be considered exploratory if the primary criteria for success is not met.

The primary analysis will be via a mixed model analysis of covariance with change from baseline to day 29 in TEWL (face) as the response variable. The model will include treatment and side of face as factors and baseline TEWL (for that side of the face) as covariate. Subject will be included as a random effect.

Within treatment means and 95% CI's will be quoted as will differences between treatments and 95% CI's, p-values for each treatment product versus control (soap only) comparison will be provided. The percentage effect of each test product versus control (soap only) will also be quoted. In the case of the assumptions underlying the model not being supported, a suitable transformation or non-parametric procedure will be used.

No imputation for missing values (due to drop out) will be used, however the likely impact will be discussed.

The MITT population will be considered primary for this analysis. Analysis of the PP population will be secondary.

There are two primary comparisons, 1 for each treatment product versus control, for success, both have to achieve statistical significance, hence no correction to the testing level is required for multiple comparisons.

12.2.7 Secondary Analysis(es)

Secondary variables include change from baseline in face and leg TEWL at Days 15 and 29 and Corneometer values at 30 minutes and 6 hours (Day 1) and 24 hours (Day 2) following first

Protocol Number: 209638 Draft Clinical Protocol

single supervised test product use and Days 15 and 29. These will be analysed in an identical fashion to that detailed in the primary analysis.

Other variables include change from baseline in TEWL and corneometer values during the regression phase to Days 30-34. These will be analysed in an identical fashion to that detailed in the primary analysis, with baseline value as the Day 1 value.

The change in TEWL values from pre- to post D-Squame challenge on Day 29 will be analysed in an identical fashion to that detailed in the primary analysis, with baseline value as the pre-D-Squame value. Analyses will be for values after 3, 6 and 9 discs from the face have been removed and 4, 8 and 12 discs from the legs have been removed.

The D-Squame total face disc protein values and the total leg disc protein values will be analysed between treatments, with subject as random effect, using similar methods to those for the primary endpoint.

All secondary analyses will only be conducted for the MITT population alone.

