To evaluate the impact of a repeated tape-strip challenge on skin barrier function following 4 weeks of twice-daily face and leg application of the investigational products and standard soap compared to the use of standard soap only.	Change from pre-challenge TEWL at Day 29 to the following time points: Removal of 3 tape strips (face) and 4 tape strips (legs); Removal of 6 tape strips (face) and 8 tape strips (legs); Removal of 9 tape strips (face) and 12 tape strips (legs). (Face: area 3 compared to area 4; leg: area 7 compared to area 8)
To evaluate the impact of a repeated tape-strip challenge on skin barrier integrity following 4 weeks of twice-daily face and leg application of the investigational products and standard soap compared to the use of standard soap only.	Total protein content extracted from all tape-strips: (Face: area 3 compared to area 4; leg: area 7 compared to area 8)
Safety	
To evaluate local tolerance.	Frequency and severity of adverse events.

Protocol Number: 209638 Draft Clinical Protocol

Study Design

This is a randomized, evaluator-blind, single-centre, two treatment regimen (test product 1 and test product 2), controlled (standard cleanser soap use only), split-body (left and right; side of the face and lower legs), parallel group clinical study designed to evaluate the impact of 4-weeks of twice-daily topical application of two developmental moisturizing cream formulations on skin barrier function in healthy subjects with dry, sensitive skin on the face and lower legs.

The chosen application sites are the face and the lower legs. The legs will be designated right and left, and the face will be split to right or left side.

There will be two treatment regimens included in this study;

- Treatment Regimen 1 = Test Product 1 + Standard Soap
- Treatment Regimen 2 = Test Product 2 + Standard Soap

Instrumental measurements of skin barrier function (TEWL; using a Tewameter) and skin moisturization (using a Corneometer) will be performed at specified time points. These measurements have been included to objectively model skin barrier function and moisturization throughout the product use and regression periods of this study.

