There will be no cleansing/standard soap use or study product application in the morning of each of the assessment study site visits (i.e. visits 3, 4, and 5) of the treatment phase. Subjects will be permitted to wash their face and legs with tap water only as needed, but not within 2 hours of the visit time. Study product application (moisturizer only) will be performed under site supervision following Corneometer assessments at Day 2 (Visit 3), and TEWL and Corneometer assessments at Day 15 (Visit 4) There will be no product application at Day 29 (Visit 5). Last application will be by the subjects at home on the evening of Day 28±2 days.

During the treatment phase, TEWL will be measured at Areas 1 and 2 (face) and Areas 5 and 6 (legs) on Day 1 at baseline (pre-product application) and on Day 15 (Visit 4), and Day 29 (Visit 5). Moisturization will be measured at Areas 1 and 2 (face) and Areas 5 and 6 (legs) on Day 1 at baseline (pre-product application), 30 minutes and 6 hours post first supervised application, on Day 2 (Visit 3), Day 15 (Visit 4), and Day 29 (Visit 5).

These measurements have been included to objectively model skin moisturization and barrier function throughout the product use and regression periods of this study.

Protocol Number: 209638 Draft Clinical Protocol

The D-Squame physical challenge will be conducted at Areas 3 and 4 (face) and Areas 7 and 8 (legs) at Day 29 (Visit 5). These areas will be subject to the sequential application and removal of D-Squame adhesive discs; 3, 6, and 9 discs will be removed from the right and left side of the face and 4, 8, 12 discs removed from the right and left leg. TEWL will be measured prior to tape-stripping and after each set of 3 (face) or 4 (leg) discs. The amount of protein recovered by each disc will also be measured with a SquameScan device (Lu *et al*, 2014).

A regression period of 6 days during which subjects will only use the standard soap twice-daily on their face and lower legs will also start on Day 29 (Visit 5). Subjects will return their assigned study product at Day 29 (Visit 5).

During the regression phase, TEWL and moisturization will be measured at Areas 1 and 2 (face) and Areas 5 and 6 (legs) on Days 30, 31, 32, 33 and 34 (Visits 6-10).

Day 34 (Visit 10) is the final assessment day and subjects will exit the study after all procedures and assessments have been completed. The soap dish and diary cards will be returned at this visit.

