9.2.1 Trans-Epidermal Water Loss

Subjects will be acclimatised in a controlled environment (temperature 20-22°C, relative humidity 40-60%) for a period of at least 30 minutes before the instrumental assessments are performed (at each time point) (EEMCO, 1997).

TEWL measurements will be taken on different parts of each designated area on each location (face and legs) so the measured parts do not overlap. Measurements will be taken in triplicate for Area 1 and 2 of the face and Area 5 and 6 on the legs and in duplicate on the D-Squame Challenge area; Area 3 and 4 of the face and Area 7 and 8 of the legs. The average (mean) reading will be taken for each area and each time point. TEWL will be measured throughout the study period per the study schedule.

Additionally, TEWL will be measured prior to the D-Squame challenge at Area 3 and Area 4 on the face and Area 7 and Area 8 on the legs. The four designated D-Squame sites will then be stripped with repeated application and removal of D-Squame discs. TEWL will be measured after the removal of 3, 6 and 9 discs from the face and 4, 8 and 12 discs for the legs.

The same operator should be used throughout the study for any given measurement, in order to reduce the variability.

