4.5 Analysis of Secondary Objectives

All secondary analyses will be conducted only on MITT population.

No alpha adjustments will be made for multiple secondary endpoints due to the exploratory nature of the inferences. All statistical tests of hypothesis will be similar to that mentioned for primary analysis and will be two-sided with 0.05 level of significance.

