Change from baseline in TEWL (face and legs) at Day 30, 31, 32, 33, and 34

The summary ([Table 14.2.4.1.1](#) for face and [Table 14.2.4.2.1](#) for legs) and statistical analysis ([Table 14.2.4.1.2](#) for face and [Table 14.2.4.2.2](#) for legs) of this endpoint will be performed in a similar fashion to the primary analysis.

The TEWL (face and legs) measurements at Day 30, 31, 32, 33, and 34 will be listed in [Listing 16.2.6.1](#).

Change from baseline in Corneometer measurements (face and legs) at Day 30, 31, 32, 33, and 34

The summary ([Table 14.2.5.1.1](#) for face and [Table 14.2.5.2.1](#) for legs) and statistical analysis ([Table 14.2.5.1.2](#) for face and [Table 14.2.5.2.2](#) for legs) of this endpoint will be performed in a similar fashion to the primary analysis. The analysis will be performed separately at each visit.

The listing of Corneometer measurements at Day 30, 31, 32, 33, and 34 will be listed in [Listing 16.2.6.2](#) for all randomized subjects.

Change from pre-challenge TEWL (face and legs) at Day 29

The change in TEWL values from pre- to post D-Squame challenge on Day 29 will be summarized descriptively ([Table 14.2.6.1.1](#) for face and [Table 14.2.6.2.1](#) for legs) and statistically analyzed ([Table 14.2.6.1.2](#) for face and [Table 14.2.6.2.2](#) for legs) similar to the primary analysis, with baseline value as the pre- D-Squame value. Summarization and analyses will be for values after 3, 6, and 9 discs removed from the face and 4, 8, and 12 discs removed from the legs.

The percentage difference between each test product + standard cleanser soap and standard cleanser soap (only) for TEWL value will be presented at removal of 3, 6 and 9 discs. The percentage difference will be obtained using following formulae:

$100 * [\text{Adjusted mean difference in each test product + standard cleanser soap and standard cleanser soap (only)}] / \text{Adjusted Mean of TEWL value for standard cleanser soap (only)}$.

The denominator of above formulae will be obtained by mixed model ANCOVA with absolute value as response variable and pre- D-Squame TEWL value as covariate. This model will be fitted for standard cleanser soap (only).

The listing of pre-challenge and post-challenge TEWL measurements at Day 29 will be listed in [Listing 16.2.6.3.1](#) for face and [Listing 16.2.6.3.2](#) for legs for all randomized subjects.

Total protein content

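### The tape-strip ANCOVA adjusts for a TEWL reading taken after four weeks of one-sided treatment, so it need not estimate the difference in change that the endpoint states

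*Protocol*

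**What the plan says.** The endpoint in the protocol's objectives table (sections 1 and 3) is "Change from pre-challenge TEWL at Day 29 to the following time points" (after each set of strips), product side against soap side, at areas 3 and 4 on the face and 7 and 8 on the legs. SAP section 4.4.2.7 lists it as secondary variable 7.

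Protocol section 12.2.7 states that this change "will be analysed in an identical fashion to that detailed in the primary analysis, with baseline value as the pre-D-Squame value". SAP section 4.5.1 has it analysed "similar to the primary analysis, with baseline value as the pre- D-Squame value", and SAP section 3.1 defines the challenge baseline as the Day 29 reading before stripping. The primary model is in protocol section 12.2.6: "The model will include treatment and side of face as factors and baseline TEWL (for that side of the face) as covariate", with subject as a random effect. Taken together, pre-challenge TEWL is both the origin of the change score and the ANCOVA covariate.

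Protocol sections 4.1 and 8.1.10 schedule Day 1 TEWL only at areas 1, 2, 5 and 6, so the challenge areas have no pre-treatment reading.

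**The concern.** In the primary analysis the covariate is read on Day 1, before any product, so randomisation balances it between sides. Here it is read on Day 29, after twice-daily product on one randomised side. It is itself an outcome of treatment. The study's success criterion is that product lowers Day 29 facial TEWL, and section 12.1 expects larger effects on the leg. If the primary succeeds, this covariate should differ between sides.

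Adjusting for it compares the sides at equal starting TEWL. That is a different question from the difference in change. Neither document names it, and randomisation does not protect it. At stake is the TEWL evidence that the products help skin resist physical insult: 3 strip levels × 2 sites × 2 products = 12 tests.

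**Working it through.** **1. The plan's own figure.** Protocol section 12.1 gives a face difference of -1.24, root MSE 2.199, 60 subjects, two-sided 5% and about 86% power. With 2.199 as the per-side residual SD, the SE of the paired difference is 2.199 × √2 / √60 = 0.401, and 1.24 / 0.401 = 3.09. The noncentral t with 59 df gives 85.9%, which matches. Reading 2.199 as the SD of the paired difference gives 99.0%, so it is the residual SD. This checks the inputs; the concern does not rest on it.

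**2. Algebra.** Let D be the randomised difference in change, P the treatment effect on pre-challenge TEWL, and b the model slope of change on pre-challenge TEWL. Then

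adjusted difference = D − b × P.

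The two agree only if P = 0 or b = 0. Taking P = -1.24 (stated for areas 1 and 2; carrying it to the adjacent areas 3 and 4 is an assumption):

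| b | shift = −b × (−1.24) |
|---|---|
| -0.5 | -0.62 |
| -0.3 | -0.37 |
| -0.1 | -0.12 |
| 0 | 0 |
| +0.3 | +0.37 |
| +0.5 | +0.62 |

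A negative shift favours the product.

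**3. Sign of b.** An error in the pre-challenge reading enters the covariate with a plus and the change with a minus, so reading error alone makes b negative. The within-subject slope is −s² / (side variance + s²), with s² the error variance of the averaged reading. For example, assume side SD 1.5 and single-reading error SD 1.0. Averaging duplicates (protocol section 9.2.1) gives s² = 0.5, slope −0.5 / 2.75 = −0.18 and shift −0.18 × 1.24 = −0.23. Between-subject variation pulls the fitted slope nearer zero. If instead the rise truly grows with starting TEWL, b is pushed upward and the shift goes against the product.

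**4. Simulation of the planned model** (illustrative). 60 subjects per product; arm, side, covariate and random subject; REML; 3,000 replicates per cell; Monte Carlo SE about 0.4 to 0.9 points. Assumed: side SD 1.5, rise SD 2.0, between-subject TEWL SD 1 or 3, between-subject rise SD 1.5 or 4.

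*No product effect on the rise*, false-positive rate at nominal 5%:

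| Error SD | SD of a single reading | SD of the averaged value |
|---|---|---|
| 0.5 | 4.2–4.7% | 5.5–6.4% |
| 1.0 | 5.0–7.4% | 7.1–13.0% |
| 1.5 | 6.4–12.6% | 9.7–21.9% |

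Without the covariate the rate is 4.1–6.0%; with a Day 1 covariate (assumed side correlation 0.6) it is 4.2–6.3%.

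As a plausibility check, the error share of the pilot MSE (2.199² = 4.836) for a change of two triplicate means is (2/3) × SD² / 4.836, ignoring baseline adjustment. Single-reading SDs of 0.5, 1.0 and 1.5 give 3%, 14% and 31%. An averaged-value SD of 1.5 means a single-reading variance of 4.5, hence 62%, so the last column's top figures are an upper-end case.

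*Rise depends on starting TEWL* by 0.3 or 0.5 per unit, single-reading error SD 0.5. The randomised difference is 0.3 × (−1.24) = −0.37 or 0.5 × (−1.24) = −0.62. The adjusted estimate is −0.03 to −0.10. Rejection is 4.9–5.7% with the covariate, against 17.1–18.8% and 34.5–39.0% without it.

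**5. Other assumed values.** With between-subject SD 3, side SD 1.8, error SD 0.9, subject SD of change 2.0 and residual SD of change 1.0 (1,500 runs), the true difference was set to 0. The rise depended on underlying untreated TEWL by −0.3, 0 or +0.3. The planned model gave −0.46, −0.12 and +0.21, with rejection 42%, 7% and 10%. Without the covariate the means were 0.00 to 0.01 and rejection 3.9–4.7%. Setting P = 0 restored the planned model (mean 0.000, rejection 5.0%), so the shift comes from the treatment effect on the covariate.

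**The case against.** The strongest reply is that the objectives table states a variable and the areas compared, not whether the contrast is marginal or conditional; the prespecified ANCOVA is the only text on estimation. If product affects the rise only by lowering starting TEWL, a comparison at equal starting TEWL may be the more informative test of resistance to insult, and the unadjusted difference would partly repeat the Day 29 result. On that reading, the rejection contrast in the second simulation reflects two questions and is not lost power for one. This much stands: the conditional question is legitimate. But neither document poses it or plans a tested comparison without the covariate, and conditioning on a treatment outcome forfeits the protection of randomisation.

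Size is also uncertain. The documents give no slope, reading-error SD or leg effect, and with modest reading error alone the inflation is negligible. That is right, and the rates above are scenarios.

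Consequences are limited too. The variable has no part in the success criterion, and SAP section 4.5 says "No alpha adjustments will be made for multiple secondary endpoints due to the exploratory nature of the inferences". The SAP also tabulates raw pre-to-post change by arm. Those tables carry no between-arm interval or test, however. Protocol section 12.2.6 and SAP section 4.4.2 call secondary analyses exploratory only if the primary criterion fails, whereas the covariate problem is most expected when it succeeds.

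**Conclusion.** The concern holds. The mechanism is certain: the planned contrast departs from the randomised difference in change by −b × P whenever product alters pre-challenge TEWL and b is not zero. With P = −1.24 on the face that is 0.12 to 0.62 g/m²/h for slopes of 0.1 to 0.5 in size, towards the product if b is negative and against it if b is positive. Direction and size cannot be settled from the documents, and the leg has no stated effect to insert. The primary analysis and the total-protein analysis are unaffected. It should be fixed before unblinding; it does not threaten the trial's main conclusion.

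**What to change.** In protocol section 12.2.7 and SAP section 4.5.1, analyse change from pre-challenge TEWL with treatment arm and side as factors and subject as a random effect, without the pre-challenge covariate. SAP section 4.5.1 already uses this structure for total protein. An acceptable alternative is the same side's Day 1 TEWL from the neighbouring area (1 or 2 on the face, 5 or 6 on the leg) as covariate. Name one of the two in advance. The planned model may stay as a sensitivity analysis, labelled as a comparison at equal starting TEWL.

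Keep the pre-challenge value as the origin of the change score in SAP section 3.1. The soap-only model for the percentage-difference denominator can stay as it is. If only the SAP is changed, add a row to its Table 5-1.

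The cost is wording; no new data are needed. In the main simulations the spread of the covariate-free estimate was between about 7% smaller and 5% larger than the planned model's. A stronger dependence of the rise on starting TEWL than the 0 to 0.5 assumed there could cost more precision.
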